8 STATISTICS AND DATA ANALYSIS

Sample size

This is a non-interventional, exploratory study, the results of which we hope will may inform a future interventional study. The primary aims are two-fold:

- a. To understand the distribution of LUTS score in patients undergoing renal transplantation
- b. To describe the distribution of LUTS scores across adverse outcomes post-transplant

Our sample size has been chosen based on three factors:

1. Feasibility within the anticipated timescale
2. The likelihood of obtaining a representative distribution of LUTS scores assuming a relatively normal distribution from other feasibility studies
3. The existing literature (it'll be the largest observational study of evaluating LUTS in transplant patients, and the only one to evaluate longitudinally)

We aim to recruit 100 patients into each of the two parts of the study over two years.

The Glasgow Renal Transplant Unit performs 100-150 renal transplants annually and assesses over 200 patients per year. Conservatively, over a two year period, 100 patients could be recruited by approaching and consenting less than half of those transplanted and fewer than 25% of those assessed for transplantation.

We anticipate a 5-10% death rate (as would be standard in the transplant population). We do not anticipate that patients will be lost to follow-up as they all come back to regular post-transplant clinics, but assuming 5-10% withdraw or have incomplete data sets that should still leave a minimum of 40 men and 40 women with complete datasets for evaluation.

There is little data on the prevalence or distribution of LUTS in the renal transplant population in men¹⁵⁻¹⁷, and no data in women. Based on the previous two year's data from our own center we anticipate that between 50-60% of patients will have one of the composite urological complication outcomes. (We have deliberately chosen a broad definition of "urological complications", with high prevalence, for this initial study so that

all possible relevant outcomes are considered so that all relevant outcomes are considered and recorded. This could be refined for future interventional studies to be more specific if deemed appropriate.)

We aim to describe both IPSS (male) and ICIQ-FLUTS (female) in combination and separately. We would therefore hope to achieve roughly similar numbers of males and females recruited into the study. We'd therefore aim to evaluate recruitment after 70 patients and if gender distribution were unequal, target as required.

We anticipate it should be large enough to allow for 5-10% death rate (as would be standard in the transplant population). We do not anticipate that patients will be lost to follow-up as they all come back to regular post-transplant clinics but assuming 5-10% withdraw or have incomplete data sets. This is primarily an exploratory study. Little data exists about the prevalence of LUTS in renal/kidney transplant recipients. It is anticipated that the results of this study will inform sample size calculations for future interventional studies.

Data collection

All data will be collected within a password protected Microsoft Excel spreadsheet stored on an NHS-password protected computer. No patient identifiable information will be included within that spreadsheet only unique patient identifiers.

Data analysis

Data analysis will be exploratory with the primary aims of describing the distribution of LUTS scores for males and females and determining the prevalence of urological complications. These factors could inform sample size calculation, determine the correct primary endpoint for a future interventional study.

If appropriate, we may/ may not attempt to:

- Investigate the relationship between LUTS severity and urological complications
- Describe any change in LUTS whilst on the transplant waiting list/ post-transplant
- Establish a risk model for urological complications post-transplant.

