6. PARTICIPANT ELIGIBILITY CRITERIA

Inclusion criteria

All adult patients (≥ 18 years old) scheduled to undergo first time renal transplantation (both deceased and living donor candidates).

Exclusion criteria

- Unable or unwilling to provide consent
- Patients undergoing re-transplant (to avoid confounding because of previous interventions)
- Patients undergoing simultaneous urological reconstructive procedures
- Patients with previously reconstructed bladders (includes Augmentation cystoplasty, ileal conduit, neobladder etc.)
- Significant cognitive impairment which would limit their capacity to accurately report symptoms

In line with NIHR guidance on equality, diversity and inclusion all people regardless of gender, sexual orientation, pregnancy, ethnicity, religion and socioeconomic status will be offered the same opportunity to participate. Hospital translators will be used where appropriate to obtain consent and the HR-QoL tools employed are available in a large variety of languages. Where it may not be possible to provide a translated HR-QoL tool, this will not serve as a contraindication to participation should the patient wish to, rather this secondary outcome measure will be omitted from data collection.

Both for equity and for scientific integrity, it's important that roughly equal numbers of men and women complete the study (as men will complete an IPSS and woman a ICIQ-FLUTS). Recruitment will be reviewed after 70 patients and patients targeted based on gender to ensure a fairly equal number of male and female participants.

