7. TRIAL PROCEDURES

This is a prospective, single center, longitudinal cohort study. Two separate patient cohorts will be considered:

3. Those approached for consent at time of transplant: baseline, 6 weeks post-transplant and 1-year post transplant measurements will be obtained
4. Those approached for consent at time of wait-listing: baseline values at time of wait-listing, time of transplant, 6 weeks and 1 year post transplant will be obtained.

Patients will be recruited over a two-year period and followed-up until they are one year post-transplant; removed from the transplant waiting list or have died.

We aim to approach all patients at the time of transplant and at the time of transplant wait-listing to offer participation.

This is primarily an observational study. History, examination and all perioperative follow-up will be conducted as would be standard of care. No additional hospital visits are required as the transplant assessment visit, transplantation, 6 week and 12 month follow-up visits will all coincide with regular clinical care.

Recruitment

Participant identification

Participants will be identified by a member of the clinical team either at time of referral for transplantation or at the time an offer of a kidney transplant offer is made. A member of the research team will be contacted and the patient screened for eligibility.

Screening

Case note review of patients' past medical and vascular access history will be undertaken by the research team to determine if eligibility criteria are met. If eligibility criteria are met, a PIS will be provided and the patient offered the opportunity to discuss the study further with the research team.

If a patient is screened but is not eligible for the trial, an anonymous record of the case will be kept in the screening log. The screening log will collect patient initials, age, and gender, date of screen failure and reason for screen failure. The screening log will be kept in the ISF.

Consent

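### The stated minimum of 40 men and 40 women with complete data has no margin for sex imbalance and, in Part 2, no allowance for patients who are never transplanted

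*Protocol*

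**What the plan says.** Protocol section 8 (Sample size) sets the target: "We aim to recruit 100 patients into each of the two parts of the study over two years". It then gives two losses. The first is "We anticipate a 5-10% death rate (as would be standard in the transplant population". The second appears as "assuming 5-10% withdraw or have incomplete data sets". Other loss is set aside: "We do not anticipate that patients will be lost to follow-up as they all come back to regular post-transplant clinics". From these it concludes "that should still leave a minimum of 40 men and 40 women with complete datasets for evaluation".

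On balance between the sexes, section 6 says: "Recruitment will be reviewed after 70 patients and patients targeted based on gender to ensure a fairly equal number of male and female participants". Section 8 likewise hopes only for similar numbers and would target recruitment if they proved unequal. No quota is set.

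Part 2 recruits at wait-listing (section 4), although the visit schedule in section 7 labels its enrolment visit as transplant assessment. Its full set of visits includes 6 weeks and 1 year after transplant. Section 7 says patients will be "followed-up until they are one year post-transplant; removed from the transplant waiting list or have died", so the protocol foresees participants whose follow-up ends without a transplant.

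For throughput, section 8 states: "The Glasgow Renal Transplant Unit performs 100-150 renal transplants annually and assesses over 200 patients per year".

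**The concern.** A figure called a minimum should hold under the least favourable conditions the protocol itself allows. This one appears to hold only under the most favourable sex split. It also carries an attrition allowance designed for people who have already been transplanted over to a cohort enrolled before transplant. The death rate is that of the transplant population, and the argument against loss to follow-up rests on post-transplant clinics. Neither covers a Part 2 participant who is taken off the list or dies waiting.

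This is the only quantified yield in the sample-size section. Men and women complete different questionnaires, and the scores are to be described by sex as well as in combination, so the number per sex sets the precision of the sex-specific results. The study is also meant to inform the size of a later trial, so its expected yield should be stated realistically.

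**Working it through.** **Inputs (protocol section 8 unless noted).** Recruits per part: 100. Deaths: 5-10%. Withdrawn or incomplete: 5-10%. Loss to follow-up: none expected. Sex split: approximately equal, with a review after 70 (also section 6). Unit activity: 100-150 transplants and over 200 assessments a year.

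**Step 1. Reproduce the stated figure.** Complete = 100 × (1 − deaths − withdrawn), or 100 × (1 − deaths) × (1 − withdrawn).
- Upper limits: 100 − 10 − 10 = 80, or 100 × 0.90 × 0.90 = 81. Halved: 40 or 40.5 per sex.
- Lower limits: 100 − 5 − 5 = 90. Halved: 45 per sex.

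The stated 40 and 40 therefore comes from one part of 100 at the upper loss limits, split evenly. The arithmetic is right.

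**Step 2. Margin for sex imbalance.** Smallest share of completers that still gives 40 in the smaller sex:
- 80 complete: 40/80 = 50.0%
- 81 complete: 40/81 = 49.4%
- 90 complete: 40/90 = 44.4%

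Number in the smaller sex:

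| Split | 80 complete | 90 complete |
|---|---|---|
| 50:50 | 40 | 45 |
| 45:55 | 36 | 40.5 |
| 40:60 | 32 | 36 |

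**Step 3. What the review after 70 can do.** Taking the 70 as counted within one part, 30 places remain. A 42:28 split at review needs 50 − 28 = 22 of the last 30 from the smaller sex. Balance can be restored as long as the larger sex has at most 50 of the first 70 (71%).

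**Step 4. Part 2, with a share t eventually transplanted.** Complete = 100 × t × (1 − other loss), and half of that per sex at an exact 50:50 split.

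| t | Per sex, 20% other loss | Per sex, 10% other loss |
|---|---|---|
| 1.00 | 40 | 45 |
| 0.95 | 38 | 42.8 |
| 0.90 | 36 | 40.5 |
| 0.75 | 30 | 33.8 |
| 0.50 | 20 | 22.5 |

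At 20% other loss, any non-transplantation takes the figure below 40. At 10% other loss, 45 × t = 40 gives t = 0.889, so it fails once more than about 11% are never transplanted. This result does not depend on the unit's activity figures.

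**Step 5. An illustrative range for t.** The crude ratio of transplants to assessments is at most 100/200 = 0.50 to 150/200 = 0.75. Used as an assumption, it gives 100 × 0.50 × 0.80 = 40 to 100 × 0.75 × 0.81 = 61 complete in Part 2, or about 20-30 per sex.

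**Step 6. Precision.** The 95% half-width for a proportion of 50% is 1.96 × √(0.25/n): 15.5 percentage points at n = 40 and 21.9 at n = 20.

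**The case against.** The strongest points on the other side are these.

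- **The study is exploratory.** It has no hypothesis, power or decision rule, and its size rests on feasibility. This stands. The consequence is lower precision in some post-transplant descriptions, not loss of power. Baseline scores are unaffected by what happens later, and change while waiting can be measured before any transplant.
- **The review after 70 is corrective.** This stands for Part 1: balance can usually be recovered. It is not guaranteed, because no quota is set and the text does not say whether the 70 is counted per part or overall.
- **Exact balance is needed only at the upper loss limits.** This is true; at 5% plus 5% a split of about 44:56 still gives 40. But a minimum has to cover the upper limits.
- **Patients never transplanted might fall under incomplete datasets.** The protocol does not say so. At the upper limits that allowance is already fully used to reach 40.
- **The figure might be pooled over both parts.** With 160 complete of 200, a smaller-sex share of 40/160 = 25% would suffice. However, 80 follows from 100 per part, and nothing in the text indicates pooling.

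A reader might go further and infer that the unit's activity caps the Part 2 yield at 50-75%. The documents do not support that. The denominator is patients assessed, some of whom are never listed, while Part 2 is mainly described as enrolling at listing; both counts may also include re-transplants, which the study excludes. A reader might also count patients still waiting as lost. Follow-up is open-ended, so they are delayed; only those never transplanted are lost to the post-transplant set. Nor does the number per sex govern every analysis, since scores are also described in combination and complications and graft function do not depend on the sex-specific questionnaire.

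**Conclusion.** The concern holds as a misstated yield. The 40 and 40 reproduces, but as the result of exact balance at the upper loss limits, with nothing in reserve. In Part 1 it is attainable but not assured: 36 in the smaller sex at 45:55 and 32 at 40:60, with 80 complete. It would be too strong to say that Part 1 fails.

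Part 2 is the clearer fault, because a foreseeable loss is left out altogether. With even recruitment, the figure falls short at any level of non-transplantation when other loss is 20%, and above about 11% when it is 10%. The range of 20-30 per sex rests on the assumed 50-75% transplanted and is illustrative only. The conclusion as a whole rests on reading the figure per part and on a complete dataset including the post-transplant visits.

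**What to change.** Restate the yield in section 8 by part.

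- **Part 1:** about 40 per sex if recruitment is balanced, with the lower figure under plausible imbalance alongside it (for example 36 at 45:55 or 32 at 40:60).
- **Part 2:** the same figure multiplied by an explicitly stated share expected to be transplanted, shown over a range and preferably taken from the unit's own listing data.
- **Both parts:** state that the baseline LUTS description keeps all recruits with a baseline score, and that only the post-transplant objectives use the smaller set.

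This is a change of wording. It needs no extra patients, no calendar cut-off for follow-up and no fixed sex quota. The only cost is a less favourable stated figure.

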9 ETHICAL AND REGULATORY CONSIDERATIONS

Research Ethics Committee

The trial protocol and study documents have been reviewed and received a favourable opinion from XXX (REC).

Substantial amendments that require review by REC will not be implemented until the REC grants a favourable opinion for the trial (amendments may also need to be reviewed and approved by the NHS R&D departments before they can be implemented in practice at local sites).

All correspondence with the REC will be retained by the CI.

An annual progress report will be submitted to the REC within 30 days of the anniversary date on which the favourable opinion was given, and annually until the trial is declared ended. It is the Chief Investigator's responsibility to produce the annual reports as required.

The Chief Investigator will notify the REC of the end of the trial.

If the trial is ended prematurely, the Chief Investigator will notify the REC, including the reasons for the premature termination.

Within one year after the end of the trial, the Chief Investigator will submit a final report to the REC with the results, including any publications/abstracts.

Other Regulatory Review

The trial shall not commence until a favourable ethical opinion has been obtained from the Research Ethics Committee and the Regulatory "Green Light" given by the Sponsor NHS Greater Glasgow and Clyde.

For any substantial amendment to the study the Chief Investigator, in agreement with the sponsor and the Study Steering Committee, will submit information to the REC for review and approval. The Chief Investigator or designee will work with the local R&D department so the necessary arrangements can be put in place to implement the amendment to confirm their support for the study as amended.

Within 90 days after the end of the study, the Chief Investigator will, on behalf of the Sponsor, ensure that the REC is notified that the study has finished. If the study is terminated prematurely, those reports will be made within 15 days after the end of the study.

The Chief Investigator will supply the Sponsor with a summary report of the clinical study, which will then be submitted to the REC within one year after the end of the study.

Peer review

The project was reviewed by two experts ([name], Consultant Transplant Surgeon, Queen Elizabeth Hospital, Glasgow and [name], Consultant Transplant Surgeon, Queen Elizabeth University Hospital, Glasgow). It was also reviewed by the West of Scotland Renal Patient Involvement and Engagement group.

Assessment and management of risk

This is essentially an observational study. It is not anticipated that patients will be subjected to any additional investigations over and above those of standard care. The rate of “filling cystoscopy”, invasive urodynamics and any complications arising from the same will be monitored by the Trial Steering Committee at 3-6 monthly intervals throughout the trial. Any change in the rates of these procedures arising within the trial, will be discussed with the Chief Investigator.

Patient Involvement and Engagement

PPIE is integral to the design, implementation, governance and dissemination of this study ensuring that the question being asked is important, outcomes appropriate and design acceptable to potential participants. PPIE undertaken in line with INVOLVE (2013) values and principles.

The study protocol and Patient Information documentation was discussed at the West of Scotland Renal Patient and Public Engagement Group and received positive feedback. The comments received have been taken into account to design this protocol.

Data protection and participant confidentiality

All investigators will comply with the requirements of the Data Protection Act 2018 and the General Data Protection Regulations (GDPR) with regards to the collection, storage, processing and disclosure of personal information and will uphold the Act's core principles.

All patients will be assigned a unique patient identifier. All data will be stored within a single Excel file on a password protected NHS computer. Patient identifiable information (name, date of birth, CHI/ NHS number, address) will be recorded in the enrolment log and retained in the ISF. This is the only place where patient identifiable information will be recorded. Secure storage of ISFs at individual sites will be the responsibility of the PI. Original consent forms will be retained within the ISF. These forms will be available to regulatory bodies and sponsor for inspection upon request.

Patient questionnaires will be scanned into patient case notes following coding within the Excel spreadsheet and will form part of the patient's clinical record. At the end of the study the original questionnaires will be destroyed. Anonymised data will be archived within a recognised data repository at the end of the study.

Indemnity

This is a clinician-initiated study sponsored by NHS Greater Glasgow and Clyde. The sponsor is a member of the Clinical Negligence and Other Risks Indemnity Scheme (CNORIS) which covers the Sponsors legal liability in relation to clinical research, this includes clinical negligence and harm from study design.

Participants who sustain injury and wish to make a claim for compensation should do so in writing in the first instance to the CI, who will pass the claim to the Sponsor's Insurers, via the Sponsor's office.

Access to the final study dataset

The final study dataset will be deposited in the UK Data Archives and be made available to researchers with an interest in the outcomes.

10 DISSEMINATION POLICY

Dissemination policy

Ownership of the results resides equally with the three primary investigators. On completion of the study, the data will be analysed and a Final Study Report prepared for REC +/- any funders. All collaborators will have the right to publish from the data. No time limits are on publication from the publication from the data.

All participants of the study will be given the opportunity to read the final report in advance and comment on it. The project team will endeavour to take their feedback into account in the final draft of the final report. Data from the final report will be available through UK Data Archives.

Results will be presented at national and international transplant conferences as well as within the Patient Forum of UK Kidney Week. Scientific publication will take place in peer reviewed journals. Additionally infographics will be created summarising key results and disseminated via patient groups and charities e.g. Kidney Research UK and Kidney Care UK

- 15 Cockett ATK. The International Consultation on Benign Prostatic Hyperplasia. Paris, France: World Health Organization, 1992.

APPENDIX 1

Procedure for undertaking bladder filling in patients who are anuric/ significantly oliguric/ unable to provide enough sample

Indication: Any patient who is anuric, passes <250ml (a cupful of urine per day) or feels bladder is full to void with <130ml on pre-void bladder scan

Procedure: A small (ideally 12F) catheter (single use or long-term) is inserted into the bladder and the bladder filled *passively* with 250ml of sterile saline. It is important that the bladder is filled passively and the saline bag is not squeezed. Once the bladder has 250ml of saline contained within, urine flow studies will be performed as standard. The bladder will be emptied with the same catheter if the patient is unable to void themselves. In case patient reports severe discomfort whilst filling the bladder, the procedure should be stopped and can be reattempted later.

If catheter insertion is unsuccessful: A flexible cystoscope can be used as an alternative to gain access to the bladder. If it is not possible to insert either catheter or flexible cystoscope, the operating surgeon should be contacted (as formal urological input may be required to facilitate catheterization pre-transplantation), documentation made in the patient notes and the test consider equivocal.

Recording results: The pre- and post-void bladder scan results and trace from the flow dynamics study should be included within the *nursing notes* (so that the trace can be scanned into the clinical portal)

Abnormal/ equivocal findings:

For equivocal bedside tests carried out on the day of transplantation, the operating surgeon should be informed of any equivocal results, but transplantation should proceed as anticipated with view to early post-operative Urology referral for consideration of Urodynamics.

For equivocal bed side tests carried out in pre-assessment clinic, transplant listing should be delayed until satisfactory Urology opinion has been obtained after due investigations.
